6.3 Dose Modifications for Selinexor

See Section 18 (Appendix 16) for supportive care and dose modification recommendations during the Maintenance Phase of the study (Version ≥3.2).

Toxicity will be graded according to NCI CTCAE, v.4.03; the therapy modifications described below are applied according to this severity grading.

If more than one different type of toxicity occurs concurrently, the most severe grade will determine the modification.

Re-escalation of the study drug is only allowed as outlined in the sections that apply for the specific toxicity. If toxicity requires a treatment delay of more than 4 weeks the patient is taken off protocol treatment.

Each dose modification or treatment delay has to be documented in the eCR, including the respective reason.

Based on observations from the ongoing Phase 1 studies in patients with advanced hematological and solid tumors, selinexor (KPT-330) shows a wide therapeutic range, with documented anti-cancer activity from ~ 12 mg/m² to ≥ 50 mg/m² orally twice weekly. At the time of Part 1 it could not be predicted which patient's tumors would respond to lower doses, nor could tolerability be predicted. Therefore, in order to individualize and optimize therapeutic benefit with selinexor, initiation of study therapy occurred at a dose just below the MTD (50 mg/m² twice weekly by mouth). To optimize specific anti-tumor activity and the patient's tolerability, dose and/or schedule modifications were allowed. Based on preliminary findings from this study and other studies, the dosing in Part 2 was modified as follows: Part 2 Schedule 1 to 35 mg/m² twice weekly, Part 2 Schedule 1 to 50 mg/m² once weekly. Dose modifications are allowed as described in Table 2 and Table 3.

Patients should also be treated aggressively with supportive care to reduce toxicities.

Patients will continue to receive selinexor until they need to have their dose reduced below the 35 mg/m² once weekly (reduced) dose in Part 1 and Part 2 (Schedules 1 and 2), at which time treatment will be discontinued.

Table 2: Pre-specified Dose/Schedule Modifications for AEs Related to Study Drug in Part 1

Dose Level	Dose of Selinexor
Dose level 0	50 mg/m ² twice weekly (D1, D3)
Dose level -1	35 mg/m ² twice weekly (D1, D3)
Dose level -2	50 mg/m ² once weekly (D1)
Dose level -3	35 mg/m ² once weekly (D1)
Dose level -4	Discontinue dosing ^a

^a Patient discontinues treatment, but continues to be assessed.

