Table 3: Pre-specified Dose/Schedule Modifications for AEs Related to Study Drug in Part 2

Dose Level	Schedule 1	Schedule 2
Dose level 0 (Starting dose)	35 mg/m ² twice weekly	50 mg/m ² once weekly
Dose level -1	50 mg/m ² once weekly	35 mg/m ² once weekly
Dose level -2	35 mg/m ² once weekly	Discontinue dosing ^a
Dose level -3	Discontinue dosing ^a	Not applicable

^a Patient discontinues treatment, but continues to be assessed.

6.3.1 Inpatient Dose Escalation:

Inpatient dose escalation can be considered after 12 weeks for patients in Part 1 and after 6 weeks for patients in Part 2 if the patient has not experienced a major toxicity; this requires approval of the Sponsor. Inpatient dose escalations will be permitted as follows:

Part 1: Dose increase to 60 mg/m² twice weekly in each week of a 4-week cycle.

Part 2 Schedule 1: Dose increase to 50 mg/m² twice weekly in each week of a 4-week cycle (8 doses total).

Part 2 Schedule 2: Dose increase to 60 mg/m² once weekly in each week of a 4-week cycle (4 doses total).

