6.3.2 Dose Adjustment Guidelines for Selinexor-Related Toxicities

Table 4: Criteria for Dose Adjustments for Selinexor-related Toxicities

Toxicity and Intensity	Dose Modification		
	Part 1: 50 mg/m ² twice weekly	Part 2, Schedule 1: 35 mg/m ² twice weekly – Ovarian only	Part 2, Schedule 2: 50 mg/m ² once weekly – Ovarian only
Fatigue (common)			
Grade 1	Ensure adequate caloric intake and assess volume status. Adjust other medications. Rule out other causes of fatigue such as electrolyte imbalance, hyperglycemia.	Ensure adequate caloric intake and assess volume status. Adjust other medications. Rule out other causes of fatigue such as electrolyte imbalance, hyperglycemia.	Ensure adequate caloric intake and assess volume status. Adjust other medications. Rule out other causes of fatigue such as electrolyte imbalance, hyperglycemia.
Grade 2	
 1. As in grade 1 2. Consider patient diary to evaluate fluid and food intake. 3. Add medroxyprogesterone acetate (MPA) (ovarian and cervical only) or 4 mg dexamethasone (or equivalent) on day after selinexor dosing. 4. In case of dehydration add IV fluids on the dosing day. 5. If fatigue does not resolve to grade 1 or baseline, reduce one dose level of selinexor 6. For additional support see NCCN guidelines^a. 	
 1. As in grade 1 2. Consider patient diary to evaluate fluid and food intake. 3. Add MPA or 4 mg dexamethasone (or equivalent) on day after selinexor dosing. 4. In case of dehydration add IV fluids on the dosing day. 5. If fatigue does not resolve to grade 1 or baseline, reduce one dose level of selinexor 6. For additional support see NCCN guidelines^a. 	
 1. As in grade 1 2. Consider patient diary to evaluate fluid and food intake. 3. Add MPA or 4 mg dexamethasone (or equivalent) 3 days post dosing of selinexor. 4. In case of dehydration add IV fluids on the dosing day. 5. If fatigue does not resolve to grade 1 or baseline, reduce one dose level of selinexor 6. For additional support see NCCN guidelines^a.

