Grade ≥ 3 without bleeding	
First occurrence: Delay selinexor treatment until resolved to ≤ grade 1 or baseline (max 4 weeks), and restart at 50 mg/m² once a week. Thrombocyte growth factors (e.g., romiplostim, eltrombopag, oprelvekin) are recommended.
 
Second occurrence: Delay selinexor treatment until resolved to ≤ grade 1 or baseline (max 4 weeks), and restart at 35 mg/m² once a week. Start treatment with thrombocyte growth factors.
 
Third occurrence: stop treatment
	
First occurrence: Delay selinexor treatment until resolved to ≤ grade 1 or baseline (max 4 weeks), and restart at 50 mg/m² once a week. Thrombocyte growth factors (e.g., romiplostim, eltrombopag, oprelvekin) are recommended.
 
Second occurrence: Delay selinexor treatment until resolved to ≤ grade 1 or baseline (max 4 weeks), and restart at 35 mg/m² once a week. Start treatment with thrombocyte growth factors.
 
Third occurrence: stop treatment
	
First occurrence: Delay selinexor treatment until resolved to ≤ grade 1 or baseline (max 4 weeks), and restart at 35 mg/m² once a week. Thrombocyte growth factors (e.g., romiplostim, eltrombopag, oprelvekin) are recommended.
 
Second occurrence: Delay selinexor treatment until resolved to ≤ grade 1 or baseline (max 4 weeks), and restart at 35 mg/m² once a week. Start treatment with thrombocyte growth factors.
 
Third occurrence: stop treatment

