
≥ Grade 3 Thrombocytopenia associated with purpura or bleeding
	
 1. Delay selinexor treatment until resolved to ≤ grade 1 or baseline (max 4 weeks), and restart at 35 mg/m² once a week. 2. Transfuse platelets per institutional guidelines. If medically indicated, discontinue any anti-platelet agents. Implement platelet growth factors and/or transfusions. Platelet growth factors may require 2-4 weeks to take effect, and should be maintained until platelets are consistently > 100,000/mm³. 	
 1. Delay selinexor treatment until resolved to ≤ grade 1 or baseline (max 4 weeks), and restart at 35 mg/m² once a week. Transfuse platelets per institutional guidelines. If medically indicated, discontinue any anti-platelet agents. Implement platelet growth factors and/or transfusions. Platelet growth factors may require 2-4 weeks to take effect, and should be maintained until platelets are consistently > 100,000/mm³. 2. When purpura or bruising resolves, restart selinexor at level -1. 	
 1. Delay selinexor treatment until resolved to ≤ grade 1 or baseline (max 4 weeks), and restart at 35 mg/m² once a week. Transfuse platelets per institutional guidelines. If medically indicated, discontinue any anti-platelet agents. Implement platelet growth factors and/or transfusions. Platelet growth factors may require 2-4 weeks to take effect, and should be maintained until platelets are consistently > 100,000/mm³. 2. When purpura or bruising resolves, restart selinexor at level -1.

Platelet Stimulators
	
The use of platelet stimulators is encouraged in patients with a history of thrombocytopenia or compromised marrow function, or in patients in whom selinexor is having demonstrable disease control. IL-11 (oprelvekin), eltrombopag, or romiplostin should be considered.
	
The use of platelet stimulators is encouraged in patients with a history of thrombocytopenia or compromised marrow function, or in patients in whom selinexor is having demonstrable disease control. IL-11 (oprelvekin), eltrombopag, or romiplostin should be considered.
	
The use of platelet stimulators is encouraged in patients with a history of thrombocytopenia or compromised marrow function, or in patients in whom selinexor is having demonstrable disease control. IL-11 (oprelvekin), eltrombopag, or romiplostin should be considered.

Hyponatremia (common)
			

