^cNational Comprehensive Cancer Network[®]. NCCN Clinical Practice Guidelines in Oncology (NCCN Guidelines[®]): Antiemesis, version 1.2015. Fort Washington, NY. April 2015. Available at: http://www.nccn.org/professionals/physician_gls/PDF/antiemesis.pdf. Attached as Appendix 10.

For patients whose dose has been reduced due to neutropenia, anorexia or fatigue, dose re-escalation is permitted if the institution of supportive care measures has reduced these toxicities to Grade ≤ 1 or to baseline for at least 2 weeks. Dose re-escalation is only permitted for these adverse events when supportive measures have been successful.

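### Table 4 gives two restart doses for a Schedule 1 patient with bleeding thrombocytopenia, and its fixed first-occurrence restart can raise the dose of Part 1 and Schedule 1 patients already at 35 mg/m² once weekly

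*Protocol*

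**What the plan says.** Protocol Section 6.3 sets the dose ladders. In Part 1 (Table 2), levels 0 to -3 are 50 mg/m² twice weekly, 35 twice weekly, 50 once weekly and 35 once weekly. Table 3, headed "Pre-specified Dose/Schedule Modifications for AEs Related to Study Drug in Part 2", gives Schedule 1 as 35 twice weekly, 50 once weekly and 35 once weekly, and Schedule 2 as 50 then 35 once weekly. The step after 35 once weekly is always discontinuation.

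Table 4 (Section 6.3.2) heads its columns by starting dose, for example "Part 2, Schedule 1: 35 mg/m ² twice weekly – Ovarian only". For Grade 3 or worse thrombocytopenia without bleeding, the first-occurrence instruction in the Part 1 and Schedule 1 columns is to delay treatment until recovery, "max 4 weeks), and restart at 50 mg/m² once a week". The second occurrence restarts at 35 once weekly and the third stops treatment. Schedule 2 restarts at 35 once weekly at both the first and the second occurrence.

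For thrombocytopenia with purpura or bleeding, step 1 in every column reads "max 4 weeks), and restart at 35 mg/m² once a week". The Schedule 1 and Schedule 2 columns add a step 2: "When purpura or bruising resolves, restart selinexor at level -1".

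On raising a dose again, Section 6.3 says "Re-escalation of the study drug is only allowed as outlined in the sections that apply for the specific toxicity". The note after Table 4 says "For patients whose dose has been reduced due to neutropenia, anorexia or fatigue, dose re-escalation is permitted", on condition that supportive care has controlled the toxicity, and adds "Dose re-escalation is only permitted for these adverse events when supportive measures have been successful". Thrombocytopenia is not named there.

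**The concern.** A restart dose after a severe platelet event should be unambiguous and should not exceed the dose at which the event happened. Table 4 misses the first aim in the Schedule 1 bleeding cell and, read literally, the second in the Part 1 and Schedule 1 cells without bleeding.

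In the bleeding cell, a site following the protocol has to choose between two doses after a bleed, even for a patient at the Schedule 1 starting dose. In the row without bleeding, the fixed figure suits patients who enter the row from the starting dose. Patients can reach 35 mg/m² once weekly before any platelet event, through reductions for other toxicities. For them, a site that follows the cell and a site that follows the re-escalation limits would give different doses after the same event.

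**Working it through.** The protocol states no figure of its own here. The check compares each restart dose with every permitted current dose, as weekly dose (mg/m² per dose × doses per week).

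**Inputs.** Tables 2 and 3 for the ladders; Section 6.3.1 for the escalated doses (Part 1 60 twice weekly, Schedule 1 50 twice weekly, Schedule 2 60 once weekly); Table 4 for the restarts.

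**Row without bleeding, first occurrence.** Change = (restart − current) / current.

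| Group (weekly restart) | Current weekly dose | Change |
|---|---|---|
| Part 1 (50) | 120, 100, 70 | −58%, −50%, −29% |
| Part 1 (50) | 50 (level -2) | 0% |
| Part 1 (50) | 35 (level -3) | (50 − 35)/35 = +43% |
| Schedule 1 (50) | 100, 70 | −50%, −29% |
| Schedule 1 (50) | 50 (level -1) | 0% |
| Schedule 1 (50) | 35 (level -2) | +43% |
| Schedule 2 (35) | 60, 50 | −42%, −30% |
| Schedule 2 (35) | 35 (level -1) | 0% |

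Of 12 permitted doses, 7 give a cut, 3 an unchanged restart and 2 a literal rise. With a clause preventing a higher restart, the two rises become unchanged restarts at 35: 7 cuts, 5 unchanged, 0 rises.

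**Is the rise allowed elsewhere?** Section 6.3 permits re-escalation only where the text for that toxicity outlines it, and the thrombocytopenia row describes none. The note after Table 4 names neutropenia, anorexia and fatigue. A patient reduced for fatigue might qualify under that note, but only once supportive care has controlled the fatigue. The platelet cell does not test that condition.

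**A second route to 35 once weekly.** Section 6.3.6 allows a move to once-weekly dosing after tumor shrinkage of at least 50%. Assuming the amount per dose is kept, a Schedule 1 patient on 35 twice weekly moves to 35 once weekly and meets the same literal rise without any earlier toxicity.

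**Bleeding row.** In Schedule 1, step 1 gives 35 per week and step 2 gives level -1 = 50 per week: 50/35 = 1.43. From the starting dose of 70 per week the cut is 50% under step 1 and 29% under step 2. From 35 per week, step 1 leaves the dose unchanged and step 2 raises it by 43%. In Schedule 2, level -1 is 35 once weekly, so the two steps agree. Part 1 names only 35 once weekly. Step 2 would also give a Schedule 1 patient who bled the same dose as a first event without bleeding. 35 once weekly is therefore the coherent reading.

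**The case against.** The strongest reply is that the 43% rise appears only when one cell is read alone. Section 6.3.2 bases modifications on the worst preceding toxicity, Section 6.3 limits re-escalation, and Section 3.1.1 allows consultation with a sponsor representative. A careful site would hold 35 once weekly. This lowers the chance of harm, but none of these provisions names a restart dose, and they do not settle which of the two doses in the Schedule 1 bleeding cell applies. The two steps there might be taken as a sequence, 35 first and 50 later. Both are worded as restarts, however, and the cell describes no re-escalation.

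Three stronger readings are tempting and should not be adopted.

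- *The row fails everyone on once-weekly dosing.* It does not. Schedule 2 patients on 50 or 60 once weekly are cut by 30% or 42%.
- *An unchanged restart at 50 once weekly is an error.* It may be intended. Schedule 2 itself repeats 35 once weekly, alongside a treatment hold and growth factors. The change rationale in Appendix 18 calls thrombocytopenia time dependent and favors lower dosing frequency. Forcing 35 at the first event would only bring the single cut forward: 50, 35, 35, stop in place of 50, 50, 35, stop.
- *The Schedule 2 cells for Grade 3 other events and Grade 2 diarrhea need the same repair.* A one-level reduction for other events would force a patient at 35 once weekly to stop, and would restart a patient escalated to 60 once weekly at 50, where the cell now gives 35. A return to the pre-event dose after diarrhea would restart that escalated patient at 60, where the cell now gives 50.

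**Conclusion.** Two errors in the dosing rules stand. The Schedule 1 bleeding cell gives two restart doses that differ by a factor of 1.43. This follows directly from Tables 3 and 4 and needs no assumption about the patient's current dose. The first-occurrence restart without bleeding, read literally, is 43% higher for patients at Part 1 level -3 or Schedule 1 level -2, against the protocol's own re-escalation limits.

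Severity is minor. Section 1.4 reports 3 patients on treatment in July 2016. Under Appendix 16 they transfer to the Maintenance Phase after their current cycle. There, a held dose may be reintroduced one level lower after consultation with the Medical Monitor. Section 6.5.2 describes bleeding with thrombocytopenia as rare. The counts above are of rules, not patients: the documents do not say how many patients sat at each level. A reader might infer that patients were actually restarted too high, or that the efficacy results are affected. The documents show neither, and these cells do not enter the endpoint definitions or the planned analyses.

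**What to change.** 1. In the Schedule 1 cell for Grade 3 or worse thrombocytopenia with purpura or bleeding, keep 35 mg/m² once weekly as the only restart dose, by deleting step 2 or correcting it to match.
2. In the row without bleeding, add after each first-occurrence restart dose: *or the dose at which the event occurred, whichever is lower*. State that lower refers to total weekly dose. Otherwise 35 twice weekly (70 per week) could be taken as lower than 50 once weekly because the single dose is smaller.

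Whether an unchanged restart at 50 once weekly is intended is for the sponsor to state. The second- and third-occurrence rules and the Schedule 2 cells for diarrhea and other events stay as they are.

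The cost is one clause and one cell edit, or a clarification letter to any site with a patient still dosed under Table 4. No procedure, visit or analysis changes.

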5.1.4 Laboratory Assessments

Blood samples will be collected as noted in [Table 1](#) and will include the analytes listed below; samples may be collected up to 3 days prior to a visit and may be repeated if clinically indicated.

- *Hematology*: hemoglobin, white blood cell (WBC) count, neutrophils, and platelets.
- *Clinical chemistry*: sodium, potassium, chloride, bicarbonate, blood urea nitrogen (BUN), creatinine, glucose, calcium, phosphate, magnesium, alanine aminotransferase (ALT), aspartate aminotransferase (AST), alkaline phosphatase, total bilirubin, lactate dehydrogenase (LDH), total protein, and albumin.

- *Urinalysis*: urine bilirubin, glucose, hemoglobin, ketones, pH, and protein.
- *Coagulation test*: prothrombin time (PT), international normalization ratio (INR), and activated partial thromboplastin time (aPTT).
- CA-125 (Ovarian cancer patients only)

5.2 **Maintenance Phase (Continued Access to Treatment and Survival Follow-up following Termination of the Primary Treatment Phase)**

See Section 18 (Appendix 16) for a description of the investigational plan (including the schedule of assessments) for the Maintenance Phase of the study (protocol version ≥3.2).

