
Grade 1 (Lower Limit of Normal to 130 nM)
	
Maintain dose level, assure adequate fluid, electrolyte and caloric intake, adjust other medications, consider salt supplementation, rule out other causes.
	
Maintain dose level, assure adequate fluid, electrolyte and caloric intake, adjust other medications, consider salt supplementation, rule out other causes.
	
Maintain dose level, assure adequate fluid, electrolyte and caloric intake, adjust other medications, consider salt supplementation, rule out other causes.

Grade ≥ 3 (120-130 nM)
	
Discontinue selinexor until resolved to grade ≤ 1, then reduce dose by 1 level. Check renal function, serum, and urinary electrolytes, and rule out other causes.
	
Discontinue selinexor until resolved to grade ≤ 1, then reduce dose by 1 level. Check renal function, serum, and urinary electrolytes, and rule out other causes.
	
Discontinue selinexor until resolved to grade ≤ 1, then reduce dose by 1 level. Check renal function, serum, and urinary electrolytes, and rule out other causes.

AST or ALT (rare)
			

Grade 1 (> ULN - 2.5 x ULN)
	
Maintain dose level
	
Maintain dose level
	
Maintain dose level

Grade 2 (> 2.5 - 5.0 x ULN)	Delay selinexor until resolved to grade \leq 1 or baseline, then maintain dose level. Consider addition of S-adenosylmethionine (SAM) 400 mg qd-bid.	Delay selinexor until resolved to grade \leq 1 or baseline, then maintain dose level. Consider addition of S-adenosylmethionine (SAM) 400 mg qd-bid.	Delay selinexor until resolved to grade \leq 1 or baseline, then maintain dose level. Consider addition of S-adenosylmethionine (SAM) 400 mg qd-bid.

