Grade 3 (> 5.0 - 20.0 x ULN)	
 1. Delay selinexor until resolved to \leq grade 2 or baseline, then reduce by 1 dose level (Table 2 & Table 3) 2. Consider addition of S-adenosylmethionine (SAM) 400 mg qd-qid. 3. If no further AST or ALT elevations occur during one cycle (4 weeks) at the reduced dose level, then dose may be continued at the reduced dose. 4. Discontinuation of selinexor is required if concurrent elevations of direct bilirubin > 2.0 X upper limit of normal (ULN) and ALT or AST > 3.0 X ULN are observed. 5. In order to characterize hepatic toxicity more precisely, fractionation of bilirubin and alkaline phosphatases will be required for elevated values > 2.0 X ULN and \geq CTCAE grade 2, respectively. 	
 1. Delay selinexor until resolved to \leq grade 2 or baseline, then reduce by 1 dose level (Table 2 & Table 3) 2. Consider addition of S-adenosylmethionine (SAM) 400 mg qd-qid. 3. If no further AST or ALT elevations occur during one cycle (4 weeks) at the reduced dose level, then dose may be continued at the reduced dose. 4. Discontinuation of selinexor is required if concurrent elevations of direct bilirubin > 2.0 X upper limit of normal (ULN) and ALT or AST > 3.0 X ULN are observed. 5. In order to characterize hepatic toxicity more precisely, fractionation of bilirubin and alkaline phosphatases will be required for elevated values > 2.0 X ULN and \geq CTCAE grade 2, respectively. 	
 1. Delay selinexor until resolved to \leq grade 2 or baseline, then reduce by 1 dose level (Table 2 & Table 3) 2. Consider addition of S-adenosylmethionine (SAM) 400 mg qd-qid. 3. If no further AST or ALT elevations occur during one cycle (4 weeks) at the reduced dose level, then dose may be continued at the reduced dose. 4. Discontinuation of selinexor is required if concurrent elevations of direct bilirubin > 2.0 X upper limit of normal (ULN) and ALT or AST > 3.0 X ULN are observed. In order to characterize hepatic toxicity more precisely, fractionation of bilirubin and alkaline phosphatases will be required for elevated values > 2.0 X ULN and \geq CTCAE grade 2, respectively.
Grade 4 (> 20.0 x ULN)	Delay selinexor until resolved to \leq grade 2, then reduce by 2 dose levels.	Delay selinexor until resolved to \leq grade 2, then reduce by 2 dose levels.	N/A
Diarrhea (common)			

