Grade 1 (despite maximal anti-diarrheal medication)	At the first sign of abdominal cramping, loose stools, or onset of diarrhea, it is recommended that the patient be treated according to institutional standard of care. Maintain dose level of selinexor.	At the first sign of abdominal cramping, loose stools, or onset of diarrhea, it is recommended that the patient be treated according to institutional standard of care. Maintain dose level of selinexor.	At the first sign of abdominal cramping, loose stools, or onset of diarrhea, it is recommended that the patient be treated according to institutional standard of care. Maintain dose level of selinexor.

Grade 2 (despite maximal anti-diarrheal medication)	First occurrence: reduce selinexor to once weekly until resolved to ≤ grade 1, then re-start twice weekly at the current dose level. Second occurrence: reduce selinexor dose by one dose level and dose once weekly until resolved to ≤ grade 1, then re-start twice weekly at reduced dose level	First occurrence: reduce to selinexor to once weekly until resolved to ≤ grade 1, then re-start twice weekly at the current dose level. Second occurrence: reduce selinexor dose by one dose level and dose once weekly until resolved to ≤ grade 1, then re-start twice weekly at reduced dose level	First occurrence: reduce selinexor to 35 mg/m ² until resolved to ≤ grade 1 or baseline, then re-start at the Dose level 0. Second occurrence: reduce one dose level
Grade 3/4 (despite maximal anti-diarrheal medication)	Delay selinexor until resolved to ≤ grade 2 or baseline, then follow guidelines above.	Delay selinexor until resolved to ≤ grade 2 or baseline, then follow guidelines above.	Delay selinexor until resolved to ≤ grade 2 or baseline then reduce one dose level.
Other selinexor-related adverse events			
Grade 1 or 2	Maintain dose level and initiate standard supportive care.	Maintain dose level and initiate standard supportive care.	Maintain dose level and initiate standard supportive care.
Grade 3	Delay dose until resolved to ≤ grade 1 or baseline, then reduce by one dose level.	Delay dose until resolved to ≤ grade 1 or baseline, then reduce by one dose level.	Delay dose until resolved to ≤ grade 1 or baseline, then reduce to Dose level -1.

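### The combined bilirubin–transaminase stopping rule is printed only in the AST/ALT Grade 3 cell of Table 4, so a site following the Grade 2 or Grade 4 row could rechallenge where the rule requires discontinuation

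*Protocol*

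**What the plan says.** Protocol section 6.3 states how Table 4 is to be used: toxicity is graded by CTCAE v4.03, and "the therapy modifications described below are applied according to this severity grading". When several toxicities occur together, "the most severe grade will determine the modification".

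In the AST/ALT block of Table 4:

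- **Grade 2** (above 2.5 to 5.0 x ULN): hold drug until grade 1 or lower "or baseline, then maintain dose level". Bilirubin is not mentioned.
- **Grade 3** (above 5.0 to 20.0 x ULN): hold, then reduce one level. Item 4 of this cell makes discontinuation mandatory when "concurrent elevations of direct bilirubin > 2.0 X upper limit of normal (ULN) and ALT or AST > 3.0 X ULN are observed". The same cell says that "fractionation of bilirubin and alkaline phosphatases will be required for elevated values", with a bilirubin threshold of 2.0 x ULN.
- **Grade 4** (above 20.0 x ULN), Part 1 and Schedule 1: hold until grade 2 or lower, then reduce two levels. Bilirubin is not mentioned.

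Item 4 and the fractionation step appear in the Grade 3 cell of all three treatment columns. They are not repeated in the notes under Table 4, in section 6.5.3 on liver enzymes, in Appendix 16 or in the SAP. The routine chemistry list in section 5.1.4 ends with "alkaline phosphatase, total bilirubin, lactate dehydrogenase (LDH), total protein, and albumin"; direct bilirubin is not on it.

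**The concern.** Item 4 acts from 3.0 x ULN, but it is printed in a row that starts above 5.0 x ULN. A patient whose ALT or AST peaks between 3.0 and 5.0 x ULN belongs to the Grade 2 row; one who exceeds 20.0 x ULN belongs to the Grade 4 row. Because the section directs sites to act by grade, a site may read only its patient's row.

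What is at stake is patient safety. For the same combined rise, one site could stop selinexor under item 4. Another could hold the drug, wait for recovery and rechallenge, at the full dose under Grade 2 or two levels down under Grade 4. The second site might never have obtained the direct bilirubin value that item 4 needs.

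**Working it through.** No sample-size or power figure is involved. The check sets the rule against each row and then looks for another provision that would supply the stop.

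**1. Where the trigger falls.** Item 4 needs ALT or AST above 3.0 x ULN. The part of that range up to 5.0 lies wholly in Grade 2, and the part above 20.0 is Grade 4. Only 5.0 to 20.0 falls in the row that prints the rule.

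**2. What each row does when direct bilirubin is also above 2.0 x ULN.**

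| Peak ALT or AST | Row | Action in that row | Item 4 |
|---|---|---|---|
| 4 x ULN (illustrative) | Grade 2 | Hold to grade 1 or baseline, then same dose | Discontinue |
| above 5.0 to 20.0 x ULN | Grade 3 | Item 4 printed here | Discontinue |
| above 20.0 x ULN | Grade 4, Part 1 and Schedule 1 | Hold to grade 2, then down two levels | Discontinue |

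Two levels down is still active treatment. In Table 2 it takes Part 1 from 50 mg/m² twice weekly to 50 mg/m² once weekly. In Table 3 it takes Schedule 1 from 35 mg/m² twice weekly to 35 mg/m² once weekly.

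**3. Whether the transaminase criterion has cleared at restart.** Under Grade 2, recovery to grade 1 means at or below 2.5 x ULN, so it has cleared. The exception is a patient restarted at a higher baseline: section 4.2.1 admits patients with known liver metastasis at AST and ALT below 5.0 x ULN. Under Grade 4, recovery to grade 2 allows restart at up to 5.0 x ULN, which can still exceed 3.0.

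**4. Whether another rule supplies the stop.** A selinexor-related bilirubin rise has no row of its own, so the most-severe-grade rule sends it to the row for other selinexor-related events. At Grade 1 or 2 that row says "Maintain dose level and initiate standard supportive care". At Grade 3 it says to hold until grade 1 or lower "or baseline, then reduce by one dose level" (Schedule 2: to level -1). Only Grade 4 says discontinue. None of these combines bilirubin with transaminases.

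**5. Whether the site will have the value.** Routine chemistry gives total bilirubin. The instruction to fractionate it is in the Grade 3 cell.

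**6. Maintenance Phase.** Section 6.3 sends dose modification to Appendix 16. Its section 1.1.2 points back to the protocol's guidelines. Its section 3.2 asks for discussion with the Medical Monitor and allows re-introduction one level lower, without naming the rule. Whether item 4 applies there is unclear.

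**The case against.** The strongest reply is that item 4 is mandatory, names no AST/ALT grade and sits one row below Grade 2 in the same block. Its 3.0 x ULN threshold suggests a general rule, and it still has work to do as printed when a Grade 3 event falls back to 3.0–5.0 x ULN. The fractionation step is likewise triggered by the bilirubin value, not by an AST/ALT grade. All of this stands: the fault is placement, and a careful investigator could apply both items at any grade. It does not remove the risk, because the Grade 2 and Grade 4 rows neither state the rule nor refer to it.

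A reader might infer that the protocol tells sites to dose through a combined liver injury. The documents do not support that. Both rows hold drug first, and under Grade 2 the transaminase criterion has normally cleared before restart. The usual exposure is rechallenge after recovery.

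Other safeguards exist. Chemistry is drawn on Days 1 and 15 of each cycle, unexplained abnormal values must be repeated and followed (section 7.1.3), and toxicity or investigator discretion can end treatment (section 5.5). They make the scenario less likely but do not restate the rule.

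A last objection is that an overriding note could force off a patient with liver metastases and a high baseline ALT whose bilirubin rises because of tumour. This is largely met: Table 4 covers selinexor-related toxicity only, and item 4 has no baseline exception as it stands. The note should nevertheless say so.

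**Conclusion.** The point holds as a misplaced safety rule that should be corrected. It is not two irreconcilable instructions, and the protocol does not lack a hepatic stopping rule.

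The number of patients affected is small and cannot be computed. Table 4 labels AST/ALT elevation rare, section 6.5.3 reports no significant liver toxicity to date, section 1.4 counts 3 patients on treatment in July 2016, and no AST/ALT event rate is given. A reader might infer a threat to the efficacy or safety results; nothing in the documents supports that, and no endpoint or statistical figure changes.

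The conclusion rests on two assumptions. First, that some sites act from their patient's grade row, as section 6.3 invites. Second, that item 4 means a permanent stop. The hyponatremia row uses the same verb for a temporary hold, but item 4 gives no condition for restarting. On the milder reading, the Grade 2 and Grade 4 rows would still set no bilirubin condition for recovery.

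**What to change.** Move item 4 and the fractionation step out of the Grade 3 cell into a stand-alone note under Table 4, where a free-standing note on isolated alkaline phosphatase already sits. The note should:

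- apply to any selinexor-related ALT or AST above 3.0 x ULN, whatever the grade, and take precedence over the grade rows;
- require fractionation whenever total bilirubin exceeds 2.0 x ULN;
- keep the baseline allowance in the Grade 2 row for transaminase rises that do not meet the bilirubin criterion;
- say whether discontinuation is permanent.

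Cross-reference the note in Appendix 16 section 3.2. Without that, the change would hardly reach the patients still on treatment, who move to the Maintenance Phase.

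The cost is a short amendment under section 11, with prior approval if it is classed as substantial, and an occasional direct bilirubin added to a chemistry sample already drawn. It could be bundled with another amendment.
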